### 5.3 REASONS NOT TO IMPLANT A STUDY IOL

At the time of cataract surgery, but prior to IOL implantation there are intraoperative adverse events that may prevent implantation of the designated IOLs for this clinical study. These criteria include, but are not limited to:

- 1) Intraoperative complications during phacoemulsification that require any other additional procedures or further intervention, e.g., vitrectomy.
- 2) Significant detachment of Descemet's membrane
- 3) Significant corneal endothelial damage
- 4) Wound burn
- 5) Capsular tear, iris incarceration or damage, posterior capsular rupture, vitreous loss or prolapse, or zonular weakness, dehiscence or rupture
- 6) Significant anterior chamber bleeding
- 7) Excessive iris mobility or need for iris manipulation
- 8) Mechanical or surgical manipulation required to enlarge the pupil prior to or at IOL implantation
- 9) Other ocular conditions or complications that could compromise IOL stability
- 10) Bag sulcus, sulcus-sulcus or unknown placement of haptics
- 11) Any method of anterior capsulotomy other than circular continuous curvilinear capsulorhexis (e.g., anterior capsular tears or any areas of 'can-opener' capsulotomy or FLACS)
- 12) Capsular fibrosis or other opacity
- 13) Optic and/or haptic damage/amputation
- 14) Inability to fixate IOL in desired position

If an operative adverse event prevents implantation of the investigational IOL and the IOL did not touch the eye, the subject should be implanted with an approved non-study IOL instead and followed until resolution or stability of that adverse event before discontinuation from the study. Later, the subject should be followed under the Investigator's normal standard of care.

If an operative adverse event prevents implantation of the investigational IOL and the IOL touched the eye, the subject should be implanted with an approved non-study IOL (if applicable). The Investigator should follow the subject through resolution of any adverse events (AEs) and then discontinue the

subject, followed under the Investigator's normal standard of care. In this case, the subject will be included in the Safety population.

#### 5.4 SCREEN FAILURES

An enrolled subject who fails to meet eligibility criteria and/or discontinues from the study before the randomization will be considered a screen failure and exited from the study.

A subject who has failed screening will not be allowed to be rescreened.

#### 5.5 STRATEGIES FOR RECRUITMENT AND RETENTION

Study participants will be recruited from the investigator's patient population, referrals, or other outreach methods. Written recruitment materials directed to potential study participants must be approved by the overseeing IRB.

Where possible, candidate participants may be pre-screened via review of their medical charts to evaluate potential eligibility based on study inclusion/exclusion criteria. During the informed consent discussion, the potential participant's willingness and ability to meet the follow-up requirements will be evaluated. Those who elect to sign the study informed consent form (ICF) will be considered enrolled in the study and given a study identification code. At/after the time of enrollment, the subject will be evaluated at the Preoperative Visit for study eligibility based on inclusion/exclusion requirements.

Study site personnel should take the following steps to minimize the likelihood of early termination during the study:

- During the Preoperative Visit, emphasize the importance of returning for all study follow-up visits and thoroughly evaluate the study subject for potential health or motivational issues or other life circumstances that may negatively affect compliance with the study follow-up visit schedule.
- Evaluate research staff flexibility to work around personal difficulties encountered by the subject related to protocol compliance (e.g., appointment times).
- Schedule subject follow-up visits early in the visit window to facilitate rescheduling within the window, if necessary.
- Follow-up on subjects who do not return for scheduled examinations.

### 6 STUDY INTERVENTION

#### 6.1 STUDY DEVICES

##### 6.1.1 INVESTIGATIONAL DEVICE DESCRIPTION

PODEYE TORIC IOL is a posterior chamber intraocular lens intended for primary implantation in the capsular bag of the eye for visual correction of aphakia after removal of a cataractous lens in adult patients with pre-existing corneal astigmatism. The refractive power of the lens has a spherical and a cylindrical component to allow for the compensation of pre-existing corneal astigmatism. The single-piece IOL has a double-C-loop haptic design with ridge technology on the haptics to prevent sticking of the haptics to the optic. A sketch of the IOL is depicted in Figure 1 and the main specifications are summarized in Table 1.

Figure 1: PODEYE TORIC IOL

**Table 1: PODEYE TORIC specifications**

Designation	Technical Specifications
Material	Hydrophobic acrylic
Optical diameter	6.00 mm
Total diameter	11.40 mm
Optic	Biconvex aspheric aberration-correcting (-0.11 $\mu$ SA)
Haptic design	Double C-loop
Filtration	UV & Blue light
Refractive index	1.53
Abbe number	42
Angulation	5°
Spherical power	From +15.0 D to +30.0 D in 0.50 D steps
Cylindrical power (IOL plane)	1.5 D
Cylindrical power (Corneal plane)	1.03 D
Recommended corneal astigmatism correction range (based on pre-operative Keratometry values excluding SIA)	0.75-1.50 D

## **Optical Design**

PODEYE TORIC IOL is an aspheric monofocal toric IOL which provides patients with distance vision and corneal astigmatism correction. The front surface is aspherical to yield an optic with a spherical aberration of -0.11 micrometers at 5.0 mm aperture to partially compensate the positive spherical aberration of the cornea and to achieve a high contrast sensitivity of the pseudophakic eye. The cylinder correction is located on the posterior surface. The IOL displays 2 series of three physical indicators (dots, see Figure 1) visible to the surgeon during implantation, which align with the meridian of lowest dioptric power (flattest meridian).

The injector to be used for PODEYE TORIC IOL over the course of the study is [REDACTED]

---

### **6.1.2 CONTROL DEVICE DESCRIPTION**

AcrySof SA60AT Monofocal IOL from Alcon (Fort Worth, TX) is a non toric, hydrophobic, ultraviolet filtering, foldable monofocal IOL with biconvex single-piece design comprised of a central optic and 2 open-loop haptics. The optic is 6.0 mm in diameter and the lens has a total diameter of 13.0mm. The lenses will be available in powers +15.0 D to +30.0 D in 0.50 D increments.

## **6.2 DEVICE ACCOUNTABILITY AND STORAGE**

---

### **6.2.1 ACQUISITION AND ACCOUNTABILITY**

Throughout the clinical study, the Investigator will be responsible for the accounting of all test and control IOLs and will ensure that the investigational products are used in accordance with the manufacturer's manual of procedures (MOP) and directions for use (DFU).

Upon receipt of the investigational product (IP), PODEYE TORIC IOL, shipment records will be verified by comparing the Shipping Receipt Confirmation to the devices actually received at the site. If a discrepancy is noted, the Sponsor or designee must be notified immediately. Accurate records of receipt and disposition (dispensing log) of the study devices (e.g., dates, subject number) must be maintained by the Investigator or authorized site representative.

Throughout the study, the Investigator must maintain records of IP dispensed and implanted for each subject. All IP sent to the Investigator must be accounted for and in no case be used in an unauthorized manner.

The Investigator is responsible for proper disposition of all unused IP at the conclusion of the study, according to the instructions provided by the Sponsor.

The control IOLs (AcrySof SA60AT) shall be procured by the Investigator from the corresponding manufacturer (Alcon).

---

### **6.2.2 PACKAGING AND LABELING**

The PODEYE TORIC investigational lenses will be provided sterile in blisters and labeled with the lens ID, lot number, expiry date. Each IOL will bear a sticker with the following statement: 'CAUTION-- Investigational device. Limited by Federal (or United States) law to investigational use.'

The AcrySof SA60AT Monofocal IOL control lenses will be provided sterile in blisters and labeled with the lot number and expiry date along with the standard manufacturer's packaging instructions.

To maintain product sterility and integrity, the study devices will be supplied in their original packaging and used according to the appropriate device instructions.

### 6.2.3 PRODUCT STORAGE AND STABILITY

Study devices should be stored in a secure area according to the package labels.

## 6.3 MEASURES TO MINIMIZE BIAS: RANDOMIZATION AND MASKING

Subjects will be randomly assigned to receive either the investigational PODEYE TORIC CYL 1.5D IOL or the AcrySof monofocal non-toric IOL in the study eye according to the randomization schedule (1:1 ratio) provided. The randomization schedule will be computer-generated and programmed by an independent statistician who is not involved in the day-to-day conduct of the study. Randomization is to occur following the completion of informed consent and screening procedures. Randomization will be stratified by site.

To minimize bias, site personnel performing postoperative study assessments of visual performance, including manifest refraction and visual acuity, will be masked to subject treatment assignment until after the final database lock ("masked assessors"). Any unmasking of the masked assessor or any study subjects must be reported to the Sponsor. Every attempt should be made to have the same masked assessor perform the same postoperative measurements for an individual subject throughout the subject's study participation.

Subjects will also be masked to their assigned treatment group (test or control group). Any material that may indicate the subjects' assigned treatment (e.g., packaging, documents) will be removed from areas where subjects and/or masked personnel may see it. Unmasked personnel should further be instructed to avoid conversation and communication with masked personnel, subjects, and persons other than the study investigator regarding subjects' assignments, outcomes, clinical courses and all other information potentially relevant to the study and its conduct.

## 7 PARTICIPANT DISCONTINUATION/ WITHDRAWAL

### 7.1 PARTICIPANT DISCONTINUATION/ WITHDRAWAL FROM THE STUDY

Discontinued subjects are those who withdraw from the study after the study informed consent document is signed and before the final visit is completed. Subjects who sign the study consent document but fail to meet eligibility criteria or withdraw prior to randomization shall be considered discontinued due to screen failure.

A subject may be discontinued prior to the final study visit for any of the following reasons, including but not limited to:

- Screen failure
- Adverse event(s); note that subjects should be followed within the study until adverse event resolution or stability

- Investigator's request (medical decision to ensure patient safety)
- Voluntary withdrawal (subject's request)
- Death
- Study terminated by Sponsor
- Loss to follow-up

Prior to discontinuing a subject, every effort should be made to contact the subject to schedule a final study visit and obtain as much follow-up data as possible. Discontinued subjects should thereafter be followed outside of the study protocol according to the Investigator's normal standard of care.

The reason for participant discontinuation or withdrawal from the study will be recorded on the Exit Case Report Form (CRF).

Randomized subjects who do not receive a study IOL or who receive a study IOL and are discontinued or withdraw from the study afterwards will not be replaced.

## 7.2 LOST TO FOLLOW-UP

The following actions must be taken if a participant fails to return to the clinic for a required study visit:

- The site will attempt to contact the participant by telephone, electronic, or regular mail to reschedule the missed visit. At least 3 documented attempts to contact the subject must be made. If the subject does not respond to these attempts, a certified letter must be sent to the participant's last known mailing address.
- Should the participant continue to be unreachable, he or she will be considered to have withdrawn from the study with a primary reason of lost to follow-up.

These actions will be recorded in the source documents and a copy of the certified follow-up letter maintained in the source documents. The date of discontinuation for subjects lost to follow-up will be 7 calendar days after the date that the unanswered certified letter was sent.

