Postoperative visits should be scheduled according to the following visit window schedule:

- Form 1: 1-2 days after surgery on the study eye
- Form 2: 7-14 days after surgery on the study eye
- Form 3: 30-60 days after surgery on the study eye
- Form 4: 120-180 days after surgery on the study eye

Refer to the Schedule of Activities in Section 1.3 and the MOP for detailed procedures to be performed at these scheduled postoperative visits.

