6.2 STUDY POPULATION

The subject population will consist of subjects with a diagnosis of cataract with pre-existing corneal astigmatism, eligible for phacoemulsification surgery followed by IOL implantation. Eligibility for the study will be determined at the preoperative visit. If the subject gives informed consent, the subject is enrolled.

Subjects will be enrolled at up to 10 investigational sites. Investigators will be encouraged to perform cataract surgery/IOL implant for at least 20 subjects per site; no Investigator may implant more than 25% of the total number of subjects planned. Site enrollment will be closely monitored to facilitate achievement of the stated enrollment goals and an even distribution across all sites.

To allow for approximately [REDACTED] and attrition between enrolment and randomization, a total of 300 subjects will be enrolled to ensure 230 subjects, 115 test and 115 control, will be implanted. It is anticipated that 13% of the 230 subjects will not complete the study, resulting in 200 with data at the Form 4 visit.

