7.2.1 Missing Observations

If no scheduled or unscheduled visit data are available within a visit window, the visit will be considered to be missed. Imputation will be performed in the ITT and All-implanted analysis populations, as described in Section 7.4.3.

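### An unreachable subject who misses Form 1, 2 or 3 is normally withdrawn before the Form 4 window opens, with no re-contact step at Form 4 and no rule for return

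*Protocol*

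**What the plan says.** Protocol section 7.2 opens with a mandatory trigger that does not separate early visits from the primary one: "The following actions must be taken if a participant fails to return to the clinic for a required study visit". The site tries to reschedule, with a stated minimum: "At least 3 documented attempts to contact the subject must be made". If there is no response, a certified letter follows. The consequence is: "Should the participant continue to be unreachable, he or she will be considered to have withdrawn from the study", with loss to follow-up as the reason. The exit is dated by a fixed rule: "The date of discontinuation for subjects lost to follow-up will be 7 calendar days after the date that the unanswered certified letter was sent".

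Section 7.1 adds a duty that comes before exit: "Prior to discontinuing a subject, every effort should be made to contact the subject to schedule a final study visit". After discontinuation, care continues under the investigator's usual practice, outside the protocol.

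Section 8.3 closes the windows for Forms 1, 2 and 3 on days 2, 14 and 60. The primary time point is much later: "Form 4: 120-180 days after surgery on the study eye". SAP section 7.2.1 makes the window decisive: "If no scheduled or unscheduled visit data are available within a visit window, the visit will be considered to be missed". SAP section 6.2 budgets for loss from all causes together: "It is anticipated that 13% of the 230 subjects will not complete the study, resulting in 200 with data at the Form 4 visit".

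**The concern.** The primary visit comes two to four months after the early windows close. A subject who cannot be reached around an early visit may well be reachable later, yet section 7.2 settles the subject's status at the early visit. Nothing in either document then calls for a new attempt when Form 4 opens, or says what happens if the subject reappears.

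For effectiveness, a missing Form 4 value is imputed in the ITT and All-implanted analyses (Protocol 9.7, SAP 8.4.3). The predictors named in the visible SAP text are attempted toric correction, age and sex; adjacent text is redacted. For the binary endpoints, Protocol 9.7 uses only the first imputed dataset. For safety, SAP 8.1 rules out imputation, and SAP 8.5.1 counts persistent events and acuity only among eyes present at Form 4. A subject withdrawn early therefore drops out of those denominators. If people who become unreachable early differ in outcome from those who stay, these losses are informative, and some of them could have been avoided.

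**Working it through.** **The plan's own figures.** 230 × (1 − 0.13) = 200.1, which agrees with the stated 200 (SAP 6.2). Overall power is 0.94 × 0.99 × 0.99 × 0.99 = 0.912, which agrees with the stated 91% (Protocol 9.5, SAP 8.6).

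**When withdrawal falls.** Let C be the day the missed visit's window closes (Protocol 8.3) and a the days spent on attempts before the letter is sent. The documents do not give a. I assume 0 to 28 days, counted from the close of the window. Then exit day = C + a + 7, and the gap to Form 4 is 120 − exit day. The last column, 120 − 7 − C, is the value of a at which exit would reach day 120.

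| Missed visit | C | Exit day (a = 0 to 28) | Days before day 120 | a needed to reach day 120 |
|---|---|---|---|---|
| Form 1 | 2 | 9 to 37 | 111 to 83 | 111 |
| Form 2 | 14 | 21 to 49 | 99 to 71 | 99 |
| Form 3 | 60 | 67 to 95 | 53 to 25 | 53 |
| Form 4 | 180 | 187 to 215 | none: exit follows the window | – |

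Across Forms 1 to 3, exit comes 25 to 111 days before Form 4 opens. Even in the latest case, a missed Form 3 with 28 days of attempts, 180 − 95 = 85 days remain before Form 4 closes.

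**Whether a final visit at exit fills the gap.** A visit arranged under section 7.1 before day 120 lies outside the Form 4 window. Protocol 8.4 lets out-of-window visits go on the scheduled form with a deviation, but SAP 7.2.1 treats Form 4 as missed if no data fall inside the window. SAP 7.1 also requires Form 4 attendance for the per-protocol set.

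**Whether power is at stake.** Each percentage point of extra loss is 230 × 0.01 = 2.3 subjects. An assumed 1 to 5 points beyond 13% leaves 230 × 0.86 = 197.8 down to 230 × 0.82 = 188.6. For the axis endpoints, the plan's criterion is that the Clopper-Pearson upper limit reaches the target. The exact binomial probability of this for endpoint 4 (true rate 91.46%, target 90%) is:

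- 100 toric eyes: 0.989 with a one-sided 95% limit (at least 85 successes), 0.995 with a 97.5% limit (at least 84).
- 90 toric eyes: 0.991 (at least 76) and 0.996 (at least 75).

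Endpoint 3 stays above 0.999 throughout. Modest extra loss does not move these powers. The inputs for endpoint 1 are redacted, so its 0.94 could not be recomputed.

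**The case against.** The strongest reply is that section 7.2 is demanding. Only a subject who has ignored at least three documented contacts and a certified letter is withdrawn, and many such subjects will not come back. The 7 days is a dating convention, with no deadline for the letter and no cap on attempts. Section 7.1 asks for every effort at a final visit, and section 5.5 tells sites to pursue people who do not return. The sample size allows for 13% non-completion, and the tipping-point analyses run from every missing binary result as a failure to every one as a success.

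Much of this stands, and it rules out several stronger readings that a reader might infer:

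- *Any missed visit leads to early withdrawal.* It does not: after a missed Form 4, exit falls on about day 187 or later.
- *Anyone who skips an early visit is closed out.* A subject who answers is rescheduled or simply has a missed visit.
- *Return is forbidden.* The documents are silent on it; they do not bar it.
- *A definite number of eyes would be recovered.* Section 7.1 lists death, adverse events and voluntary withdrawal beside loss to follow-up. The 13% is not split by cause, and no return rate is given.
- *The study loses power.* The binary endpoints show no material change.

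What the reply does not reach is the gap itself. The efforts it cites come before exit or are general advice; none is tied to Form 4. Imputation and tipping-point analyses describe the uncertainty from missing outcomes but do not supply the outcomes. The safety endpoints measured at Form 4 have no imputation at all.

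**Conclusion.** The point holds in a limited form. For an unreachable subject who missed Form 1, 2 or 3, section 7.2 fixes withdrawal about 25 to 111 days before Form 4 opens, assuming 0 to 28 days of attempts from the close of the window. The direction is not sensitive to that assumption: after a missed Form 3, the attempts would have to last 53 days or more before exit reached day 120, and longer still after Forms 1 and 2.

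The number of subjects is unknown and probably small. All causes of non-completion together are budgeted at 0.13 × 230 = 29.9, about 15 per arm, and only some of those would leave this way and later be reachable. The cost is avoidable and possibly informative missing data at the primary time point. It deserves correction because it follows from a stated rule and is cheap to remove.

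**What to change.** Amend Protocol section 7.2 as follows:

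- For a subject who cannot be reached after missing Form 1, 2 or 3, record a missed visit and keep the subject in follow-up.
- Repeat the contact attempts when the Form 4 window opens on day 120.
- Assign lost to follow-up only if day 180 passes without a Form 4 visit, unless the subject withdraws consent or dies.
- State that a subject who returns resumes the schedule.

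The change does not recover everything. Co-primary endpoint 4 is the change in axis from Form 3 to Form 4 (Protocol 9.5). After a missed Form 3 it stays missing even if Form 4 is attended, unless an unscheduled visit inside the Form 3 window supplies the value under SAP 7.2. The other Form 4 outcomes would be measured.

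The cost is one paragraph in an amendment, a few more contact attempts per unreachable subject, and exit forms that close later.

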## 8 STUDY ASSESSMENTS AND PROCEDURES

Study participants will be evaluated at a Preoperative Visit. The subjects who qualify for further study participation will be randomized to receive the assigned study IOL, and the cataract surgery/IOL implantation will be scheduled to occur between 1 and 90 days after the Preoperative visit. The subjects will be scheduled to return for follow-up visits and examinations at the Day 1-2, Week 1-2, Month 1-2, and Month 4-6 time periods, consistent with study visits described in ISO 11979-7 (Form 0 through Form 4). Data collected from each visit, including any abnormal findings, will be documented in the source records and recorded on study eCRFs.

The timing and type of assessments/procedures to be performed at each visit is outlined in the SOA. Methods for study examinations is presented in the Manual of Procedures.

### 8.1 PREOPERATIVE VISIT (DAY -90 TO DAY -1)

The Preoperative Visit must occur no more than 90 days and no less than 1 day prior to the Operative Visit. Informed consent must be obtained prior to performing study-specific procedures not part of the

investigator's routine standard of care. Subjects who sign the ICF will be given a unique 5-digit screening number, where the first two digits correspond to the site number.

At this visit, the following activities will be performed:

1. Biometrya
  - Keratometry\*
  - Target refraction\*
  - IOL power calculation\*
  - Axial length\*
  - Anterior chamber depth\*
  - Toric Power calculation
2. Corneal Topography\*
3. Inclusion/Exclusion Criteria Evaluation
4. Demographics
5. Concomitant Medications
6. Ocular and Significant Non-ocular Medical History\*
7. Urine Pregnancy Test (if applicable)
8. Manifest Refraction (ETDRS) – 4 m\*
9. BCDVA - Photopic, Monocular (ETDRS) – 4 m\*
10. UCDVA - Photopic, Monocular (ETDRS) – 4 m\*
11. Projected Visual Acuity\*
12. Slit lamp Examination\*
13. Intraocular Pressure\*
14. Dilated pupil size\*
15. Dilated Fundus Exam\*
16. Randomization
17. Adverse Events

*\* These assessments, if performed during routine standard of care exams up to 90 days before the subject Preoperative Visit, may be used as qualifying preoperative assessments prior to consent. All study specific evaluations not included in a routine cataract evaluation must be performed in the preoperative time period (Day -90 to Day -1).*

*a Biometry (if not done during routine standard of care exams), to be done before inclusion/exclusion criteria evaluation.*

Subjects must be targeted as closely as possible to emmetropia. **For PODEYE TORIC IOL, SRK/T formula and A-constant 119.4 should be used to determine IOL power.** Surgeons may use their personalized A-constant for model SA60AT.

The SIA value an investigator will use in this study must be a predetermined single value (each investigator may use their own personal SIA value) that is reported to the sponsor at the beginning of the study and consistently used for all subjects treated by the investigator.

The subjects will be randomized in 1:1 ratio to either Study arm or control arm, as per the randomization schedule.

## 8.2 OPERATIVE VISIT (DAY 0): FORM 0

At the Operative Visit, prior to surgery, subjects will be assessed to reconfirm eligibility and any changes in concomitant medications and medical/ocular conditions will be recorded on the appropriate CRF. If the subject is determined no longer to be eligible, he/she will be discontinued from the study prior to cataract surgery.

All cataract surgical procedures will be performed by a qualified Investigator according to the Investigator's usual standard of care, using a phacoemulsification system adjusted according to the Investigator's customary settings. Surgery may be performed under either local or topical anesthesia, with or without intracameral ophthalmic anesthesia. Subjects must be targeted as closely as possible for emmetropia. Surgeons may use their personalized A-constant for model SA60AT. For PODEYE TORIC, surgeons must use the SRK/T formula and an A-constant of 119.4. The Investigator must also reference the Directions for Use for the PODEYE TORIC IOL and AcrySof SA60AT Monofocal IOL.

[REDACTED] must be used to implant the PODEYE TORIC in accordance with [REDACTED]. A qualified delivery system should be used for the AcrySof SA60AT IOL, in accordance with the Alcon Directions for Use.

[REDACTED]

[REDACTED]

No additional refractive procedures are to be performed during the operative procedure or throughout the postoperative study period. Femtosecond laser-assisted cataract surgery (FLACS) must not be performed to create corneal incisions, to adjust astigmatism during the study period, or for any other reason. (Note: Corneal incisions intended to reduce corneal astigmatism (e.g., Limbal relaxing incisions and astigmatic keratotomy are not permitted)

If operative complications prevent implantation of the investigational Study IOL (PODEYE TORIC or Control IOL) (see Section 5.3 – Reasons Not to Implant a Study IOL), a non-study IOL may be implanted instead. Subjects who were not exposed to the study IOL will be exited from the study and followed per the investigator's standard of care.

The Investigator should refer to the Manual of Procedures for more detailed guidance on PODEYE TORIC and AcrySof SA60AT implantation.

After the operative procedure but at the same visit, IOL axis orientation retro-illuminated slit lamp images must be taken for the subjects implanted with PODEYE TORIC IOL. Refer to the Manual of Procedures for more guidance.

## 8.3 POSTOPERATIVE VISITS: FORM 1 THROUGH FORM 4

Postoperative visits should be scheduled according to the following visit window schedule:

- Form 1: 1-2 days after surgery on the study eye
- Form 2: 7-14 days after surgery on the study eye
- Form 3: 30-60 days after surgery on the study eye
- Form 4: 120-180 days after surgery on the study eye

Refer to the Schedule of Activities in Section 1.3 and the MOP for detailed procedures to be performed at these scheduled postoperative visits.

